Oral suspension (mL) bid	2.0	2.5	3.0	3.5	4.0	5.0	5.5	6.0	7.0
Reduced Dose (mg) bid	13.3	16.7	20	23.3	26.7	33.3	36.7	40	46.7
Oral suspension (mL) bid	1.3	1.7	2.0	2.3	2.7	3.3	3.7	4	4.7

In addition, in case a subject will have a consistent (e.g., at least 2 consecutive evaluations) platelets count  $\leq 150 \times 10^9/L$  and not meeting the stopping criteria for platelets, the Investigator will have to reduce the dose of 1/3 of the current dose.

Moreover, for subjects who have already reduced the dose of 1/3 an additional reduction by 20% is allowed for safety reasons.

For **all subjects**, during the first month of treatment, platelets count assessment will be performed weekly, while during the second month it will be performed every 2 weeks, in order to strictly monitor this parameter for safety reasons.

If the dose is reduced due to platelet count  $\leq 150 \times 10^9/L$ , and/or white blood cell  $< 3.0 \times 10^9/L$  and/or hemoglobin  $< 10.0 \text{ mg/dL}$ , a complete blood count (i.e.CBC) test must be performed weekly for 8 consecutive weeks.

	Any decision relevant to the dose adjustment and/or modification of schedule of assessments can be discussed with the Medical Monitor, but the final decision remains with the Investigator only or its authorized designee
Other:	As the subjects to be randomised are on stable steroids, the recommended national immunisation schedule, including varicella immunity, should be completed (i.e., as recommended in the “Diagnosis and Management of Duchenne muscular dystrophy” DMD guideline  ), before the Screening Visit. However, in case of live or live attenuated vaccines to be administered during the study, the Investigator can discuss, but it is not mandatory, the case with the Medical Monitor of the study and must carefully monitor the subject.
Independent Data Monitoring Committee:	An independent Data Monitoring Committee (IDMC) will review, evaluate and categorise safety findings every 3 months during the study and will be responsible for oversight of the formal interim analysis (see below). The IDMC will have access to unblinded data, if necessary, and will operate according to the rules defined in the IDMC charter.

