### 7.3.1 *Safety Stopping Rules*

Study drug should be permanently interrupted if any of the following occurs:

- severe drug-related diarrhoea (i.e., increase of  $\geq 7$  stools per day);
- any drug-related SAE;
- QTcF  $> 500$  msec\*;
- platelets count  $\leq 50 \times 10^9/L$  (to avoid laboratory errors and anomalous values, platelets count  $\leq 50 \times 10^9/L$  must be confirmed with a repeated test performed on the next working day. The treatment should be stopped until the retest result becomes available. If the repeated platelets count is still  $\leq 50 \times 10^9/L$ , study drug must be permanently discontinued. If the repeated test is acceptable, the subject can resume treatment.);
- white blood cells  $\leq 2.0 \times 10^9/L$  (to avoid laboratory errors and anomalous values, white blood cells  $\leq 2.0 \times 10^9/L$  must be confirmed with a repeated test performed on the next working day. The treatment should be stopped until the retest result becomes available. If the repeated white blood cells is still  $\leq 2.0 \times 10^9/L$ , study drug must be permanently discontinued. If the repeated test is acceptable, the subject can resume treatment.);
- hemoglobin  $\leq 8.0$  g/dL (to avoid laboratory errors and anomalous values, hemoglobin  $\leq 8.0$  g/dL must be confirmed with a repeated test performed on the next working day. The treatment should be stopped until the retest result becomes available. If the repeated hemoglobin is still  $\leq 8.0$  g/dL, study drug must be permanently discontinued. If the repeated test is acceptable, the subject can resume treatment.).

The Investigator will follow up on him until resolution or acceptable stabilization of the event occurs and document all the relevant information, as applicable. After the resolution/stabilization of the event, the subject will be withdrawn from the study and the EOS Visit (see Section 9.1.8) will be performed.

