\* based on average QTc value of triplicate ECGs. For example, if an ECG demonstrates a prolonged QTcF interval >450msec, 2 more ECGs should be obtained over a brief period, and then the averaged QTcF values of the 3 ECGs should be used to determine whether the subjects should be discontinued from the study. If the mean QTcF value of the 3 replicates still meets the stopping criteria the subject has to interrupt the study drug, the medical monitor has to be informed and the value must be confirmed by the central reading before withdraw the subject from the study. The QTc has to be calculated with the Fridericia formula  $QTc = QT/RR^{1/3}$ .

Study drug should be temporarily stopped if any of the following occur:

- moderate or severe diarrhoea (i.e., increase more than 4 stools per day).
- platelets count  $<75 \times 10^9/L$  but  $>50 \times 10^9/L$  (the treatment should be temporarily stopped and platelets count has to be performed by 1 week and re-tested until platelets will be normalized);
- white blood cell  $<3.0 \times 10^9/L$  but  $>2.0 \times 10^9/L$  (the treatment should be temporarily stopped and white blood cells have to be measured by 1 week and re-tested until white blood cells will be normalized);
- hemoglobin  $<10.0$  g/dL but  $> 8.0$  g/dL (the treatment should be temporarily stopped and hemoglobin has to be measured by 1 week and re-tested until hemoglobin will be normalized);
- Triglycerides  $>300$  mg/dL (3.42 mmol/L) in fasting condition (the treatment should be temporarily stopped and triglycerides has to be measured every 2 weeks until triglycerides return to levels below 300 mg/dL (3.42 mmol/L);

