**Table 4: Placebo or Givinostat Dose Modification for subjects randomized under study protocol version 6.0 or 7.0 or 8.0.**

Weight (kg)	$\geq 10$ and $< 12.5$	$\geq 12.5$ and $< 20$	$\geq 20$ and $< 25$	$\geq 25$ and $< 30$	$\geq 30$ and $< 40$	$\geq 40$ and $< 50$	$\geq 50$ and $< 60$	$\geq 60$ and $< 70$	$\geq 70$
Starting Dose (mg) bid	13.3	16.7	20	23.3	26.7	33.3	36.7	40	46.7
Oral suspension (mL) bid	1.3	1.7	2.0	2.3	2.7	3.3	3.7	4	4.7
Reduced Dose (mg) bid	10.6	13.4	16	18.6	21.4	26.6	29.4	32	37.4
Oral suspension (mL) bid	1.1	1.3	1.6	1.9	2.1	2.7	2.9	3.2	3.7

Study drug can be resumed at a level 20% smaller than the dose at which the AE leading to temporary stop occurred, once platelets and/or white blood cell and/or hemoglobin are normalized and/or triglycerides return to levels below 300 mg/dL (3.42 mmol/L) or when diarrhoea is mild.

For subjects randomized under protocol version 6.0 or 7.0 or 8.0, only one dose reduction is allowed during the treatment period.

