**Dose Modification (all subjects):**

If subjects (i.e. those already in treatment or those who will be randomized under protocol version 6.0 or 7.0 or 8.0) gain weight during the study the drug dose must be kept unchanged.

If subjects (i.e. those already in treatment or those who will be randomized under protocol version 6.0 or 7.0 or 8.0) lose weight during the study, the drug dose should be adjusted

according to Table 2 or Table 3 if the subject is still on treatment at starting dose, or according to Table 4 or Table 5 if the subject has already reduced the starting dose.

All subjects will be asked to have platelets count assessments weekly during the first month of treatment and performed every two weeks during the second month of treatment, in order to strictly monitor this parameter for safety reasons.

If the dose is reduced due to platelet count  $\leq 150 \times 10^9/L$ , and/or white blood cell  $< 3.0 \times 10^9/L$  and/or hemoglobin  $< 10.0 \text{ mg/dL}$  a complete blood count (i.e.CBC) test must be performed weekly for 8 consecutive weeks.

If a dose adjustment and/or modification of schedule of assessments is decided by the Investigator or authorized designee, it is advised to discuss this decision with the Medical Monitor, however this is not mandatory as the Investigator is the only responsible for the medical care of the subject and the Investigator's decision should not be influenced, deleted nor approved by the Medical Monitor.

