6. 12-lead ECG has to be done in triplicate at the screening visit and during the other visits if an ECG demonstrates a prolonged QTcF interval  $>$  450 msec, obtain 2 more ECGs over a brief period, and then use the averaged QTcF values of the 3 ECGs to determine whether the subjects should be discontinued from the study (see Section 7.3.1). 12-lead ECG should be performed at 2,5 hours (i.e 150 minutes)  $\pm$ 30 minutes after drug intake.
7. Pulmonary function tests FEV1, FVC, FEV1/FVC and PEF. In case the test does not achieve ATS criteria and the evaluator does not feel a valid attempt has been made, the subject should repeat the test at randomization if the test is failed at screening visit. If the test is failed at 12 months and/or at 18 months the subject has to be asked to come back to perform the test.
8. Serology: immunoassay methodology for CMV IgM; in-house methodology of chemiluminescence for HBsAg/HCV/HIV; and ECLIA for EBV IgG.
9. Hematology test: CBC:RBC, WBC (including differential count), hemoglobin, MCH, MCHC, MCV, hematocrit, and platelets. Test will be done according to the schedule (i.e., weekly for the first month of treatment, every 2 weeks for the second month of treatment) and are to be performed more frequently if clinically indicated. Note: Repeat visits for the platelets count will be assumed at the request of the Investigator. If the dose is reduced due to platelet count  $\leq$ 150 x 10^9/L, and/or white blood cell  $<$ 3.0 x 10^9/L and/or hemoglobin  $<$ 10.0 mg/dL, a complete blood count (i.e.CBC) test must be performed weekly for 8 consecutive weeks.
10. The following blood tests will be assessed: total bilirubin, direct bilirubin, alkaline phosphatase, amylase, ALT, AST, LDH, cystatin C, CRP, GGT, creatine kinase, total protein, albumin, uric acid, triglycerides, phosphorus, total cholesterol, LDL, HDL, sodium, potassium, chloride, calcium, glucose, creatinine, BUN, TSH, fT3, fT4, bicarbonate). Note that TSH, fT3, and fT4 will be taken at Visits 7, 9, 10, 11, 12, 13, 14, 15 and 16.
11. Urinalysis: appearance, pH, specific gravity, protein, glucose, ketone bodies, blood and WBCs, and urobilinogen.

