#### **9.1.7 Visits 10 – 14 (Weeks 12-60, $\pm$ 7 days)**

The Visits 10, 11, 12, 13 and 14 will respectively happen after 12, 24, 36, 48 and 60 weeks after the Randomization Visit, with a visit window of  $\pm$  7 days.

At Visit 10 – 14 (i.e., every 3 months), the following assessments will be performed unless otherwise noted:

- Collect and record concomitant medications;
- Perform a physical examination;
- Measure vital signs (blood pressure, pulse rate, and body temperature);
- Measure weight;
- Measure height (only at Visits 11 and 13; i.e., after 6 and 12 months of treatment) ;
- Perform a 12-lead ECG (at 2,5 hours  $\pm$ 30 minutes after drug intake);
- Perform pulmonary function tests: FEV1, FVC, FEV1/FVC, and PEF (only at Visit 13);

Pulmonary function as assessed by spirometry at visit 13 should be repeated if the test does not meet ATS/ERS criteria and/or the evaluator deems that a valid attempt to perform a correct maneuver has not been made by the subject.

- Collect blood samples for:
  - hematology;
  - blood chemistry;
  - coagulation tests (PT and aPTT);
- Collect DMD serum biomarkers (only at Visit 13);
- Obtain a urine sample for urine analysis;
- Perform Quality of Life tests (assessed by PODCI) (only at Visit 13; i.e., after 12 months of treatment);
- Perform time to 4SC
- Perform NSAA and 6MWT;
- Perform muscle strength tests;
- Obtain PK blood sample (only at Visits 10, 11, and 13; i.e., after 3, 6, and 12 months of treatment, respectively);

- Dispense and account for study drug;
- Subject diary dispensation and evaluation of drug compliance through diary;
- Assess AEs;
- Perform MRI/MRS evaluation (MR cohort only) (only at Visit 13; i.e., after 12 months of treatment).

At Visit 13, functional tests will be video recorded.

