Factors to be considered in assessing the relationship of the AE to study drug include:

- The temporal sequence from study drug administration;
- The recovery on discontinuation and recurrence on reintroduction;
- The concomitant diseases;
- The evolution of the treated disease;
- The concomitant medication;
- The pharmacology and PK of the study drug;
- The presence of an alternative explanation.

Abnormal Laboratory Findings and Other Objective Measurements:

Abnormal laboratory findings and other objective measurements should not be routinely captured and reported as AEs as they will be collected and analysed separately in the eCRF. However, abnormal laboratory findings and other objective measurements that meet the criteria for an SAE, result in discontinuation of the study drug or require medical intervention, or are judged by the Investigator to be clinically significant changes from baseline values should be captured and reported on the AE pages of the eCRF.

When reporting an abnormal laboratory finding on the AE pages of the eCRF, a clinical diagnosis should be recorded in addition to the abnormal value itself, if this is available (for example “anaemia” in addition to “haemoglobin = 10.5 g/dl”).

Baseline Medical Condition:

Medical conditions present at the screening visit, that do not worsen in severity or frequency during the study are defined as baseline medical conditions and are not AEs. These medical conditions should be adequately documented on the appropriate page of the eCRF, i.e., the medical history page. However, medical conditions present at the initial study visits that worsen in severity or frequency during the study should be recorded and reported as AEs.

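### The haemoglobin trigger for weekly blood counts after a dose reduction is printed in mg/dL instead of g/dL in all three places, so as written it can never apply

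*Protocol*

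**What the plan says.** The rule on weekly complete blood counts (CBCs) appears three times in the protocol: in the synopsis under dose adjustment, in Section 8.2.2 under dose modification for all subjects, and in Table 6, footnote 9. It applies when the dose has been cut because platelets were at or below 150 x 10^9/L, white cells were below 3.0 x 10^9/L, or haemoglobin was below a limit. In footnote 9 that haemoglobin limit is "10.0 mg/dL, a complete blood count (i.e.CBC) test must be performed weekly for 8 consecutive weeks". The other two places give the same number and the same unit.

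Other haemoglobin values in the protocol are in grams:

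- **Temporary stop (Section 7.3.1, repeated in the synopsis):** below 10.0 but above 8.0 "g/dL (the treatment should be temporarily stopped and hemoglobin has to be measured by 1 week and re-tested until hemoglobin will be normalized".
- **Permanent stop (Section 7.3.1, repeated in the synopsis):** a value at or below 8.0 "g/dL must be confirmed with a repeated test performed on the next working day".
- **Adverse event example (Section 12.9.2):** "haemoglobin = 10.5 g/dl".

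After a temporary stop, Section 8.2.2 lets dosing resume at the lower dose "once platelets and/or white blood cell and/or hemoglobin are normalized". Nothing in the protocol, the SAP or the SAP addendum corrects the mg/dL unit.

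**The concern.** The printed limit is below any haemoglobin a treated child could have. On a literal reading, a reduction made for haemoglobin alone does not bring the eight mandatory weekly counts with it.

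No other mandatory rule covers that period. The re-testing in Section 7.3.1 runs until haemoglobin is back to normal, which is the point at which the reduced dose starts. From then on the eight weekly counts are the only specific monitoring required for a child who has just shown a haemoglobin fall on treatment. A site that followed the printed text would also record no deviation, so missed counts could go unnoticed.

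**Working it through.** **Step 1: convert the unit.** The inputs are the printed limit (10.0 mg/dL, three places), the temporary-stop upper bound (10.0 g/dL, Section 7.3.1) and the permanent-stop bound (8.0 g/dL, Section 7.3.1).

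- 10.0 mg/dL / 1000 = 0.010 g/dL
- Against the temporary-stop bound: 10.0 / 0.010 = 1000
- Against the permanent-stop bound: 8.0 / 0.010 = 800

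**Step 2: see which subjects the limb could reach.** A confirmed value at or below 8.0 g/dL leads to permanent discontinuation, not dose reduction. The threshold-defined route to a haemoglobin-driven reduction is therefore the temporary-stop band, above 8.0 and below 10.0 g/dL. Every value in that band exceeds 0.010 g/dL, so the printed condition is false for all the subjects it was meant to cover. With g/dL in its place, the limb matches the upper bound of the band exactly, which confirms the intent.

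**Step 3: count what the routine schedule would supply.** Table 6 places on-treatment haematology at weeks 1, 2, 3, 4, 6, 8, 12, 24, 36, 48, 60 and 72. Section 9.1.7 confirms the later spacing: Visits 10 to 14 "will respectively happen after 12, 24, 36, 48 and 60 weeks after the Randomization Visit". For a restart at week t, count the scheduled tests after week t and up to week t + 8.

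| Restart week | Scheduled tests in the next 8 weeks | Count | Short of 8 by |
|---|---|---|---|
| 2 | 3, 4, 6, 8 | 4 | 4 |
| 4 | 6, 8, 12 | 3 | 5 |
| 8 | 12 | 1 | 7 |
| 12 | none | 0 | 8 |
| 16 | 24 | 1 | 7 |
| 24 | none | 0 | 8 |

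From week 12 the visits are 12 weeks apart, so an 8-week window holds at most one. The count is 0 or 1 for any restart from week 12 to week 64. The windows of plus or minus 7 days do not change this: the closest two such visits can fall is 12 - 2 = 10 weeks, still more than 8.

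**The case against.** The strongest reply is that the rule is not a free-standing laboratory threshold. It applies once a dose has been reduced for a haematological reason, and the threshold that leads to a haemoglobin reduction is the one in Section 7.3.1, which is correct. The mg/dL figure only restates why a reduction already made was made. A value of 0.010 g/dL is impossible in a living child, so there is no rival clinical reading, and most sites would take it as g/dL.

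It can also be said that few subjects are likely to be involved. Section 4.2.1 names thrombocytopenia as the dose-limiting toxicity in humans, and Section 8.2.1 attributes the observed reductions to platelets. The schedule counts are a floor, because footnote 9 allows more frequent tests when clinically indicated and Section 9.1.10 allows unscheduled visits. A restart as early as week 2 is improbable, since haemoglobin would have to fall, recover and be followed by re-dosing within two weeks. Finally, the SAP addendum records changes made after database lock, so a message to sites now has limited use.

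Most of this stands and limits the weight of the point. It does not make the printed text right. The sentence is a mandatory instruction, its numerical condition is wrong wherever it appears, and discretionary testing does not replace a required test. SAP Section 5.2.1 also says that haematology was reported in SI units at EU sites and in US conventional units at US sites, so the unit is not something to leave to inference.

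**Conclusion.** The concern holds. It is a misprint, not a choice, and it is confined to the haemoglobin limb of one safety-monitoring rule. The printed limit is 1000 times too low, and read literally the limb can never trigger. The cost of a literal reading would be 4 to 8 of the 8 weekly counts for the restart weeks tabulated, and 7 or 8 for any restart from week 12 to week 64.

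Those counts assume nominal visit weeks, no extra discretionary tests, and a site that ignores the limb. The documents do not give the number of haemoglobin-only reductions and do not suggest that any site misapplied the rule, so no number of affected subjects can be stated. The platelet and white-cell limbs, the stopping rules, the dose-reduction rules and the efficacy analysis are unaffected.

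**What to change.** Replace mg/dL with g/dL in the synopsis (dose adjustment), Section 8.2.2 (dose modification, all subjects) and Table 6, footnote 9, and send sites a short clarification.

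Whatever the stage of the trial, check that every haemoglobin-driven reduction was followed by its eight weekly counts. No new data are needed: SAP Section 3.5 lists dose modifications, Section 5.1 lists adverse events leading to dose reduction, and Section 5.2.1 lists all haematology values. Any missed counts should be recorded as deviations. The sponsor should also confirm that the wording was not carried into the long-term study announced in Section 6.1, whose protocol is not available here.

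The cost is three one-word edits, one notice, and a date check in what is probably a small number of subjects.

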## 9.1 Procedures by Study Visit

There will be at least 15 study visits, including the Screening and Randomisation Visits.

Assessments will be performed as outlined in the following by-visit subsections. As platelets count reductions are observed after treatment with givinostat, study site personnel who will perform functional tests and MRI/MRS must be different from the personnel who will review subjects' safety results and safety results must not be shared with the personnel responsible for the functional tests and MRI/MRS.

At the discretion of the Investigator, subjects not meeting inclusion/exclusion criteria may be re-screened twice with an interval of at least 3 months between assessments.

If needed, safety assessments (e.g. blood test, unscheduled visits) may be performed at the subject's home by a local qualified nurse trained in the study protocol.

### 9.1.1 Visit 1 and Visit 2 - Screening (*Week -4 ± 2 weeks*)

The Screening visits (Visit 1 and Visit 2) will occur within 4 weeks ( $\pm 2$  weeks) prior to the Randomisation Visit. The following assessments will be performed at Visit 1 unless noted otherwise:

- Obtain written Informed Consent from the subject's parent/legal guardian and assent or consent from the subject, if applicable;
- Eligibility criteria: review inclusion and exclusion criteria;
- Genetic test (*only if it is not already available*);
- Collect medical history and demographic data;
- Collect and record prior medications (taken in the past 6 months);
- Perform a physical examination (at Visit 1 assessment for ankle ROM should be done);
- Measure vital signs (blood pressure, pulse rate, and body temperature);
- Measure weight;
- Measure height;
- Perform a 12-lead ECG (in triplicate);
- Perform an ECHO;
- Perform pulmonary function tests: FEV1, FVC, FEV1/FVC, and PEF;
- Collect blood samples for:
  - serology tests;

- hematology;
- blood chemistry;
- coagulation tests (prothrombin time [PT] and activated partial thromboplastin time [aPTT]);
- Obtain a urine sample for urine analysis;
- Perform Quality of Life tests (using Paediatric Outcomes Data Collection Instrument [PODCI] scores);
- Perform time to 4SC (the test should be performed at Visit 1 and at Visit 2; the 4SC at Visit 2 can be performed one day after V1 up to a maximum of 2 weeks +3 days);
- Perform NSAA and 6MWT;
- Perform muscle strength test (both by HHM and MMT);
- Perform cognitive function evaluation: Raven coloured progressive matrices (at Visit 1 or at Visit 2. Test should be performed at the beginning and at the end of the study at the same time of the day);
- Assess AEs;
- If all inclusion and exclusion criteria have been met and the subject is eligible, the following assessments must be performed at Visit 2 to conclude the screening period before the randomisation:
  - MRI/MRS

At Visit 1, functional tests will be video recorded.

Subjects will be instructed to avoid physical activity that would exceed their normal activity for 3 days before each visit.

NB: As the subjects to be randomised are on stable steroids, the recommended national immunisation schedule, including varicella immunity, should be completed (i.e., as recommended in the “Diagnosis and Management of Duchenne Muscular Dystrophy” guideline), before the Screening Visit. However, in the case of live or live attenuated vaccines to be administered during the study, the Investigator must carefully monitor the subject, and while the decision of the Investigator cannot be influenced, deleted nor approved by the Medical Monitor, it is advised but not mandatory that the Investigator discuss the case with the Medical Monitor before using these vaccines.

